8.8. Treatment with Cemiplimab Beyond Disease Progression

It is recognized that a minority of patients treated with immunotherapy may derive clinical benefit despite initial evidence of progressive disease.

Patients who experience RECIST 1.1-defined progressive disease will be permitted to continue treatment until further progression is observed, provided the following criteria are met:

- Investigator assesses continued use of a PD-1 therapy is appropriate
- Patient continues to meet all other study eligibility criteria, as defined in the inclusion/exclusion criteria (Section [7.2](#))
- Patient is tolerant of cemiplimab and has a stable performance status.
- Patient provides written informed consent prior to resuming treatment by signing the current version of the ICF (eg, the patient repeats the written informed consent that was done prior to initial study enrollment).
- Patients do not have evidence of rapidly progressing disease

It is understood that, if there is further progression after resumption of treatment ($\geq 30\%$ increase in tumor burden from the time of initial progressive disease by RECIST criteria; this includes an increase in the sum of all target lesions and/or the development of new lesions), that cemiplimab will be discontinued.

Patients should continue with assessments according to [Table 2](#).

9. STUDY SCHEDULE OF EVENTS AND PROCEDURES

9.1. Schedule of Events

Study assessments and procedures are presented by study period and visit in [Table 2](#).

The allowable window for all visit days and assessments is ± 3 business days (excluding weekends and holidays), unless otherwise stated. All other "days" in the protocol refer to calendar days. For tumor assessments (CT or MRI), the window is ± 7 days from planned scan dates, unless otherwise stated.

Missed doses of cemiplimab or visits will not be made up. In the case of missed doses of cemiplimab, tumor assessments should still follow original schedule. If a patient is unable to undergo scans within the window due to logistical or medical reasons, tumor assessment will be obtained at the next available date.

Missed doses of ISA101b are detailed in Section [8.3.1.3.1](#).

In light of the public health emergency related to COVID-19, the continuity of clinical study conduct and oversight may require implementation of temporary or alternative mechanisms. Examples of such mechanisms may include, but are not limited to, any of the following: phone contact, virtual visits, telemedicine visits, online meetings, non-invasive remote monitoring devices, use of local clinic or laboratory locations, and home visits by skilled staff. Additionally, no waivers to deviate from protocol enrollment criteria due to COVID-19 will be granted. All temporary mechanisms utilized, and deviations from planned study procedures are to be documented as being related to COVID-19 and will remain in effect only for the duration of the public health emergency.

Table 2: Schedule of Events

Study Procedure	Screening Visit ¹	Cycle 1 ^{2,3}				Cycle 2 to 4 ^{2,3}			Cycles 5+ ^{2,3}				EOT Visit ^{4,5}	Safety Follow-up ^{4,5}	Tumor Assessment ⁵	Survival Follow-up ^{4,5}
	Day -28 to Day -1	Day 1	Day 8 ±3	Day 29 ±3	Day 50 ±3	Day 1 ±3	Day 22 ±3	Day 43 ±3	Day 1 ±3	Day 22 ±3	Day 43 ±3	Day 64 ±3	30 days after last dose ±7 days	90 days after last dose ±10 days	Every 4 months (±10 days)	Every 4 months (±10 days)
Inclusion/exclusion	X															
Informed consent ⁶	X															
Genomics substudy informed consent (optional)	X															
PBMC consent (optional)	X															
Future biomedical research consent (optional)	X															
Medical history and demographics	X															
Electrocardiogram ⁷	X												X	X		
Performance status	X												X	X		
Tumor tissue sample	X ⁶															
Treatment:																
Cemiplimab (experimental) ⁸			X	X		X	X		X	X	X					
ISA101b (experimental) ^{8,9}		X		X	X											
Efficacy (Radiologic):																
CT scan and/or MRI ¹⁰	X				X			X				X	X ¹¹	X	X	
Safety:																
Weight and height (height at screening only)	X	X ¹²				X			X							
Complete physical examination ¹³	X											X				

Study Procedure	Screening Visit ¹	Cycle 1 ^{2,3}				Cycle 2 to 4 ^{2,3}				Cycles 5+ ^{2,3}				EOT Visit ^{4,5}	Safety Follow-up ^{4,5}	Tumor Assessment ⁵	Survival Follow-up ^{4,5}
	Day -28 to Day -1	Day 1	Day 8 ±3	Day 29 ±3	Day 50 ±3	Day 1 ±3	Day 22 ±3	Day 43 ±3	Day 1 ±3	Day 22 ±3	Day 43 ±3	Day 64 ±3	30 days after last dose ±7 days	90 days after last dose ±10 days	Every 4 months (±10 days)	Every 4 months (±10 days)	
Limited physical examination ¹⁴		X ¹²	X	X	X	X	X	X	X	X	X	X		X			
Vital signs ¹⁵	X	X	X	X	X	X	X	X	X	X	X	X	X	X			
Concomitant medications	X	X	X	X	X	X	X	X	X	X	X	X	X	X			
Adverse events		Continuous Monitoring for Adverse Events												X			
Phone contact																X	
Laboratory Testing:																	
Hematology ¹⁶	X	X ¹²	X	X	X	X	X	X	X	X	X	X	X	X			
Blood chemistry ¹⁶	X	X ¹²		X	X	X	X	X	X	X	X	X	X	X			
Prothrombin time Activated partial thromboplastin time	X				X			X					X				
TSH (with reflex T3, free T4)	X				X			X					X				
HBV, HCV, HIV	X																
Pregnancy test for WOCBP ¹⁷	X	X ¹²			X			X				X					
Urinalysis	X				X			X				X	X				
PK, ADA, Biomarkers:																	
PK sample (cemiplimab) ¹⁸		X				X			X				X				
ADA sample (cemiplimab) ¹⁹		X				X			X				X				
Soluble biomarkers (serum)		X	X	X									X				
ctDNA plasma sample		X		X		X											
T cell immune monitoring PBMC sample ²⁰		X	X	X		X			X				X				

Study Procedure	Screening Visit ¹	Cycle 1 ^{2,3}				Cycle 2 to 4 ^{2,3}				Cycles 5+ ^{2,3}				EOT Visit ^{4,5}	Safety Follow-up ^{4,5}	Tumor Assessment ⁵	Survival Follow-up ^{4,5}
	Day -28 to Day -1	Day 1	Day 8 ±3	Day 29 ±3	Day 50 ±3	Day 1 ±3	Day 22 ±3	Day 43 ±3	Day 1 ±3	Day 22 ±3	Day 43 ±3	Day 64 ±3	30 days after last dose ±7 days	90 days after last dose ±10 days	Every 4 months (±10 days)	Every 4 months (±10 days)	
Pharmacogenomics (optional sub-study) ²¹	X																

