6. STUDY DESIGN

6.1. Study Description and Duration

This will be a single-arm, phase 2, global study of treatment with cemiplimab + ISA101b in HPV16-positive cervical cancer patients with disease progression on first line chemotherapy in the recurrent or metastatic setting. Study treatment and duration include cemiplimab every 3 weeks (with 3 doses of ISA101b on days 1, 29, and 50) until progression or any reason for early discontinuation as outlined in Section 7.3 and Section 8.2.2.

Patients will undergo screening evaluations to determine eligibility within 28 days prior to first treatment. All patients will receive the following regimen:

- ISA101b 100 µg/peptide by SC injection on day 1, day 29, and day 50 (total of 3 doses).
- Cemiplimab 350 mg given by IV infusion over 30 minutes Q3W on days 8 and 29 in cycle 1, on days 1 and 22 in cycles 2 through 4, and on days 1, 22, and 43 in all subsequent cycles or until disease progression or discontinuation of study drug for any other reason.

[figure not shown]
Note: On days 29 and 50, cemiplimab will be administered first, and ISA101b will be administered approximately 1 hour after the end of the cemiplimab infusion. Patients must be observed for 4 hours after each ISA101b administration.

The timing of doses is summarized in Figure 2. Cycle 1 will be 7 weeks long, cycles 2 through 4 will be 6 weeks long, and all subsequent cycles will be 9 weeks long.

Patients will be assessed for response at cycle 1 day 50 (week 7), then once per cycle (every 6 weeks for 3 cycles, then every 9 weeks in all subsequent cycles or until disease progression or discontinuation of study drug for any other reason; Section 8.8, Section 8.2.2, and Section 7.3, respectively). Patients with confirmed CR after a minimum of 48 weeks of treatment may elect to discontinue treatment and continue with all relevant study assessments (eg, efficacy assessments).

There will be a 90-day safety follow-up after the last dose of cemiplimab. Patients who discontinue study drug for reasons other than progression will be followed approximately every 4 months by scans until disease progression or until the patient commences another anticancer systemic therapy, whichever comes first. After progression, survival follow-up should occur approximately every 4 months.

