The total duration of study from start of screening to final analysis of OS is expected to be approximately 36 months (approximately 12 months of accrual, approximately 12 months of treatment, and approximately 12 months of follow up).

Figure 2: Study Flow Diagram

¹ Withdrawal due to reasons as listed in Section 7.3 and Section 8.2.2.

End of treatment is defined as the end of study drug. Patients may discontinue study drug for progression of disease or for any reason listed in Section 7.3 and Section 8.2.2. Thirty days after the last dose of study drug, patients will have EOT visit. Ninety days after the last dose of study drug, patients will have the safety follow-up visit (Table 2).

A patient who progresses on treatment will have EOT visit and safety follow-up visit. End of study (EOS) disposition will be on or after the safety follow-up visit. They will then enter survival follow-up.

A patient who discontinues treatment for reasons other than progression, as listed in Section 7.3 and Section 8.2.2, will have EOT and safety follow-up visit. They will then have tumor assessments until progression or the start of another anticancer therapy. At progression or start of another anticancer therapy, patients will have EOS disposition and then enter survival follow-up.

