8.2.3. Immune-Mediated Adverse Events

8.2.3.1. Identification of Immune-mediated Adverse Events

Investigators must be extremely vigilant and be ready to intervene early in the management of imAEs, as the onset of symptoms of imAEs (eg, pneumonitis) may be subtle. An imAE can occur at any time during treatment or several months after the last dose of treatment. All AEs of unknown etiology associated with study drug exposure should be evaluated to determine possible immune etiology. If an imAE is suspected, efforts should be made to rule out neoplastic, infectious, metabolic, toxin or other etiologic causes prior to labeling an AE as an imAE.

Based on the emerging safety profile of cemiplimab and other antibodies targeting the PD-1/PD-L1 axis, working case definitions are provided in the Investigator's Brochure to help investigators distinguish imAEs from non-immune AEs commonly associated with PD-1 inhibition ([Naidoo, 2015](#)), ([Weber, 2015](#)). This is not exhaustive of all possible imAEs. Clinical presentations of less common imAEs, including neurologic, musculoskeletal, cardiac, renal, and ocular events ([Hofmann, 2016](#)), ([Zimmer, 2016](#)), should be reviewed in patients with concerning presentations.

The case definitions in the Investigator's Brochure have not been validated and are intended only as guidance for investigators to help distinguish imAEs from non-immune AEs. These definitions may evolve as clinical experience increases with cemiplimab and other antibodies targeting the PD-1/PD-L1 axis. Investigators' clinical judgment may include other factors when determining if an AE is immune-mediated.

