14. Limited physical exam includes lungs, heart, abdomen, and skin.
15. Vital signs are collected within 10 minutes prior to infusion, and approximately 15 minutes (± 10 minutes) after the completion of the infusion. Vital signs will also be taken every hour

during the 4-hour observation after administration of ISA101b. Note: Blood pressure should be measured after the patient has been resting quietly for at least 5 minutes. Blood pressure may be obtained from a seated or recumbent position and should be done consistently throughout the study. When scheduled at the same time as other procedures, vital signs should be measured prior to clinical laboratory assessments, PK, or exploratory sample collection.

16. Hematology and chemistry samples may be obtained ≤ 72 hours prior to cemiplimab treatment.
17. Pre-dose serum or urine β -human chorionic gonadotropin (HCG) up to 72 hours prior to study drug administration. Serum/urine pregnancy tests are requirements for women of child bearing potential only.
18. Serum samples for cemiplimab concentration will be collected from all patients pre-dose (C_{trough}) on cycle 1 day 1 and every other cycle for the first 2 years of treatment. After 2 years, samples for cemiplimab concentration will be collected pre-dose every 6 months (24 weeks) during therapy and at EOT.
19. ADA serum samples for cemiplimab will be collected pre-dose of cemiplimab administration on day 1 of cycle 1, and pre-dose of cemiplimab on day 1 of cycles 3 and 5 for the first year of treatment, then pre-dose every 4 cycles for the subsequent years of treatment (eg, C9, C13 and so on) and at EOT. In the event of AESI, additional samples may be collected for ADA analysis at or near the event when possible.
20. Peripheral blood mononuclear cell (PBMC) collection is optional. PBMC samples will be collected pre-dose on day 1, 8, and 29 of cycle 1, pre-dose on day 1 of cycles 2 through 4, day 1 of cycles 5+, and at end of treatment.
21. Pharmacogenomics (optional sub-study): See Section [9.2.10](#).

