9.1.3. Unscheduled Visits

All attempts should be made to keep patients on the study schedule. Unscheduled visits may be necessary to repeat testing following abnormal laboratory results, for follow-up of AEs, or for any other reason, as warranted.

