9.2.3.6. Laboratory Testing

Hematology, blood chemistry, coagulation, TSH (with reflex T3, free T4), urinalysis, and pregnancy testing samples will be analyzed by the site's local laboratory.

Samples for laboratory testing will be collected at visits according to [Table 2](#). Tests will include:

Blood Chemistry

Sodium	Glucose	Aspartate aminotransferase (AST)
Potassium	Albumin	Alanine aminotransferase (ALT)
Chloride	Total protein, serum	Alkaline phosphatase
Carbon dioxide (bicarbonate)*	Creatinine	Bilirubin (total/direct)***
Calcium	Blood urea nitrogen (BUN)**	Uric acid

*At sites at which the bicarbonate assay is not performed as part of the routine chemistry panel, it may be omitted

**At sites at which a urea assay is performed instead of BUN, the urea assay will be acceptable.

***Total or direct bilirubin may be measured, whichever is standard per site.

Hematology

Hemoglobin	Differential:
White blood cells (WBCs)	Neutrophils
Platelet count	Lymphocytes

Monocytes

Urinalysis

pH	Ketones	Glucose
Specific gravity	Protein	Blood

Other Laboratory Tests

Thyroid Function Tests: Thyroid-stimulating hormone (with reflex T3, free T4) will be tested at visits specified in [Table 2](#) while the patient is on treatment. If TSH is abnormal, T3 and free T4 should be measured at the investigative site's local laboratory. If an investigative site routinely performs total T3 and/or total T4 tests, these measurements will be acceptable in lieu of free T3 or free T4.

Coagulation Tests: Prothrombin time and activated partial thromboplastin time testing will be performed at visits specified in [Table 2](#) while the patient is on treatment. Sites may report INR and activated PTT if it is the standard of care at that site.

Viral Serology Tests: HBV, HCV, and HIV serum antibodies will be tested at visits specified in [Table 2](#).

Pregnancy Tests: Serum β -HCG or urine β -HCG will be measured ≤ 72 hours prior to study drug administration) and serum/urine β -HCG will be measured at all other time points as specified in [Table 2](#).

Abnormal Laboratory Values and Laboratory Adverse Events

All laboratory values must be reviewed by the investigator or authorized designee.

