10.1.5. Abnormal Laboratory, Vital Signs, or Electrocardiogram Results

The criteria for determining whether an abnormal objective test finding should be reported as an AE include:

- The test result is associated with accompanying symptoms, and/or

- The test result requires additional diagnostic testing or medical/surgical intervention, and/or
- The test result leads to a change in dosing (outside of protocol-stipulated dose adjustments), discontinuation from the study, significant additional concomitant drug treatment, or other therapy

Contact the medical monitor in the event the investigator feels that an abnormal test finding should be reported as an AE, although it does not meet any of the above criteria.

Repeating an abnormal test, in the absence of any of the above conditions, does not constitute an AE. Any abnormal test result that is determined to be an error does not require reporting as an AE.

Evaluation of severity of laboratory abnormalities will be assessed according to the scale outlined in Section [10.2.5](#).

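### As extracted, protocol Table 2 schedules no TSH in cycles 5+, so a patient given 48 weeks of cemiplimab goes 177 days between scheduled thyroid tests

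*Protocol*

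**What the plan says.** **Schedule.** Protocol section 9.1, Table 2, has a row "TSH (with reflex T3, free T4". In the extracted text it is marked at screening, cycle 1 day 50, day 43 of cycles 2-4 and EOT. No cycle 5+ visit (day 1, 22, 43 or 64) is marked.

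**Text rule.** Section 9.2.3.6 sets no timing of its own: "Thyroid-stimulating hormone (with reflex T3, free T4) will be tested at visits specified in" Table 2, while the patient is on treatment. None of the footnotes in section 9.1.1 adds a cycle 5+ test.

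**Treatment length.** Section 6.1 continues cemiplimab every 3 weeks until progression or discontinuation and sets no maximum. Two statements there show that treatment past week 25 is foreseen. The overall timeline is "approximately 12 months of accrual, approximately 12 months of treatment, and approximately 12 months of follow up", and "Patients with confirmed CR after a minimum of 48 weeks of treatment may elect to discontinue treatment".

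**Risk.** Section 3.3.2.2 names immune-mediated adverse events (imAEs) as an important identified risk. Section 8.2.3.1 warns that onset may be subtle and says: "An imAE can occur at any time during treatment or several months after the last dose of treatment". Appendix 2 gives separate management tables for hypothyroidism and hyperthyroidism.

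**Analysis.** SAP section 4.5.3 lists thyroid function tests among the laboratory variables. Section 5.8.2 summarises laboratory results by visit, and section 5.8.1 tabulates treatment-emergent imAEs by grade.

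**The concern.** Routine TSH follows the end-of-cycle visits through cycle 4 and then stops, while the drug that carries the thyroid risk goes on. CT, urinalysis and the pregnancy test follow the same end-of-cycle pattern and do continue, at cycle 5+ day 64. Nothing in the text explains why TSH should differ. PT/aPTT shares the blank.

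The stake is patient safety first. A patient in cycle 5 or later whose thyroid function changes without symptoms has no planned test until about a month after the last dose. The change may be found late or, if transient, not at all. The data consequence is secondary. Cycles 5+ contribute no planned thyroid values to the laboratory summaries, and some low-grade thyroid events may be missing from the imAE table.

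**Working it through.** **1. Reading the row.** Splitting the extracted rows on their column breaks gives 16 visit columns. Column 12 is cycle 5+ day 64 and column 13 is EOT.

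| Row | Marked columns |
|---|---|
| TSH | 1, 5, 8, 13 |
| PT/aPTT | 1, 5, 8, 13 |
| Urinalysis | 1, 5, 8, 12, 13 |
| CT/MRI | 1, 5, 8, 12, 13, 14, 15 |
| Pregnancy test | 1, 2, 5, 8, 12 |
| PK and ADA | 2, 6, 9, 13 |
| PBMC | 2, 3, 4, 6, 9, 13 |
| Complete physical exam | 1, 12 |

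Alignment checks in the part of the table that holds the TSH row:
- All six PBMC marks agree with footnote 20: days 1, 8 and 29 of cycle 1, then "pre-dose on day 1 of cycles 2 through 4, day 1 of cycles 5+, and at end of treatment".
- The PK and ADA rows end in column 13, and footnotes 18 and 19 name EOT.
- The phone-contact mark is in column 16, survival follow-up, as section 9.1.4 implies.
- Urinalysis has separate marks in columns 12 and 13, so day 64 and EOT are distinguished here.

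**2. Calendar.** Inputs: cycle lengths of 7, 6 and 9 weeks (footnote 2), dosing days (section 6.1), and EOT 30 days after the last dose (section 9.1.2). Dates are nominal, without visit windows.
- Cycle starts: C2 = 1 + 49 = day 50; C3 = 50 + 42 = 92; C4 = 92 + 42 = 134; C5 = 134 + 42 = 176; C6 = 176 + 63 = 239; C7 = 239 + 63 = 302; C8 = 302 + 63 = 365.
- The calendar reproduces the protocol's own assessment schedule: day 50 is week 7, then 6-week steps.
- Scheduled on-treatment TSH: days 50, 92, 134 and 176 (weeks 7, 13, 19 and 25), 42 days apart.
- Screening to day 50, with no day 0: from day -1 it is 50 - (-1) - 1 = 50 days; from day -28 it is 50 - (-28) - 1 = 77 days.

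**3. The gap.** Cemiplimab starts on day 8 and is given every 21 days, so dose n falls on day 8 + 21(n - 1). Dose 9 is day 176, dose 10 is day 197, dose 16 is day 323 and dose 17 is day 344. By the exposure formula in SAP section 5.6.2, dose 16 gives (323 - 8 + 21)/7 = 48.0 weeks.

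| Last dose | EOT | Test to test (day 176 to EOT) | Day 176 to last dose |
|---|---|---|---|
| Day 323 (48 weeks) | Day 353 | 353 - 176 = 177 days | 323 - 176 = 147 days |
| Day 344 (51 weeks) | Day 374 | 374 - 176 = 198 days | 344 - 176 = 168 days |

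In the 48-week case, doses 10 to 16 (seven doses) are given after the last routine test. The figure to compare with 42 days is 177, because both run from one test to the next.

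**4. With a day 64 test in cycles 5+.** The 48-week patient is tested on days 176 + 63 = 239, 239 + 63 = 302 and at EOT on day 353. The intervals are 63, 63 and 51 days.

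**The case against.** **The blank may be a reading artefact.** Everything rests on empty cells in a table read by a program. In the header above the TSH row, the cycle 2 to 4 label spans four cells for three listed days. In an earlier part of the table the complete physical exam is marked at cycle 5+ day 64, where a limited exam is also marked, and not at EOT. A one-column slip in that row is likely. Two further points favour a slip in the TSH row. Section 9.2.3.6 speaks of testing while the patient is on treatment, which fits day 64 better than a visit 30 days after the last dose. TSH and PT/aPTT are also the only rows with this end-of-cycle pattern that skip day 64. This stands in part. The checks above support the alignment of this part of the table, but a slip confined to these two rows cannot be excluded. A reader might infer that a drafting error in the protocol is proven; the documents do not carry that.

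**Other safeguards cover it.** Cycle 5+ visits keep vital signs, limited examination, hematology and chemistry, and AEs are monitored continuously. Section 9.1.3 says: "Unscheduled visits may be necessary to repeat testing following abnormal laboratory results, for follow-up of AEs, or for any other reason, as warranted". Appendix 2 prompts thyroid checks when an endocrine event is suspected. A reader might infer that thyroid monitoring ceases after week 25; these provisions show it does not. They do depend on symptoms or suspicion, so silent change remains uncovered.

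**The effect on reported safety is small.** A reader might infer that thyroid imAE rates would be materially understated. The documents do not support that either. Under section 10.1.5 an abnormal value counts as an AE only on stated grounds, such as "The test result requires additional diagnostic testing or medical/surgical intervention, and/or" accompanying symptoms or a change in dosing or therapy. A silent transient shift may therefore not be reportable even when found. For grade 1 thyroid events Appendix 2 asks mainly for closer monitoring. The number of patients treated past week 25 is not given, and 48 weeks is not shown to be typical.

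**Stopping may be a choice.** No section sets a TSH interval that Table 2 breaks, and the protocol already accepts 50 to 77 days from screening to the first on-treatment test. That is fair, and it shows that 63 days would be in keeping with the plan. It does not account for 177 days.

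**Conclusion.** The concern holds in a limited form. On the extracted text, routine TSH stops at day 176 while cemiplimab continues without a maximum duration. For a patient given 48 weeks of cemiplimab, 177 days separate two scheduled tests, 147 of them up to the last dose and with seven further doses. The comparison is 42 days between on-treatment tests from cycle 1 day 50 to cycle 4 day 43. A reader might set 147 against 42, or take 42 days as the spacing throughout. The first compares different measures, and the second overlooks the 50 to 77 days after screening.

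The consequence is late or missed detection of silent thyroid change in patients treated past week 25. ORR is unaffected, and no patient count or bias in event rates can be claimed. The conclusion assumes that the row is also blank in the source table, that dosing and visits are on schedule, and that no unscheduled TSH is taken.

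**What to change.** First check the TSH row, and the PT/aPTT row that shares its pattern, against the source table. If cycle 5+ day 64 is marked for TSH there, the point closes at no cost.

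If it is blank, mark TSH (with reflex T3, free T4) at day 64 of each cycle 5+, on the draw already scheduled for hematology and chemistry. On-treatment tests after day 176 are then at most 63 days apart on nominal dates. Keep the EOT test. A footnote explaining a deliberate stop would document the gap but not close it.

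The cost is one extra local assay per 9-week cycle, or two for a 48-week patient (days 239 and 302), with no new visit or blood draw.
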